12.2.8.3. Other Secondary Endpoints

Safety analyses are described in Section 12.2.13, pharmacokinetic analyses are described in Section 12.2.10, and health outcome analyses are described in Section 12.2.12.

12.2.9. Sensitivity Analysis

Sensitivity analyses will be undertaken for calculation of the primary endpoint in order to evaluate the robustness of the analysis. Of specific note, a PFS analysis with a subgroup of the ITT population whose starting dose was 150 mg will be performed as a sensitivity analysis. Details can be found in the SAP.

In addition, a PFS analysis based on independent central review data will be conducted by applying the censoring rules from Table JPBL.12.1. Details can be found in the Central Review SAP.

An additional OS analysis will also be conducted based on the following definition using similar methods as stated in Section 12.2.8: time is defined as the time from the date of study enrollment to the date of death due to disease. Survival time will be censored on the date the patient was last known to be alive for patients who have no reported event. For patients that have died due to reasons not disease related, survival time will be censored at the date of death.

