The PFS and OS analyses to test the superiority of abemaciclib to placebo in improving PFS and OS time will use the log-rank test stratified by stratification variables. Additional analyses will be performed using the Kaplan-Meier method to estimate the PFS and OS curves and rates, and the Cox proportional hazard model will be used to estimate the PFS and OS HRs and corresponding 95% confidence interval.

Safety:

All safety summaries and analyses will be based on the Safety Population. Patients will be grouped according to treatment received in Cycle 1.

Health Outcomes:

The maximum change from baseline score will be calculated and summarized for BPI “worst pain” and EORTC composite scores. The number and reason for missing and incomplete questionnaires/assessments will be summarized for each instrument and study arm.

Pharmacokinetics:

PK parameters for abemaciclib in plasma (clearance, exposure, volume of distribution, and half-lives) and inter-individual PK variability will be computed using nonlinear mixed effect modeling implemented in NONMEM. If warranted by the data, PK parameters for fulvestrant in plasma and inter-individual variability estimates will also be computed using nonlinear mixed effect modeling implemented in NONMEM.

Pharmacodynamics:

Pharmacodynamic data (such as neutrophil, lymphocytes, or platelets counts in blood) may be analyzed by means of NONMEM and connected to the population PK model for abemaciclib and/or fulvestrant in a PK/pharmacodynamic model.

Tailoring biomarkers:

Summary statistics will include means, medians, corresponding standard errors, quartiles, and ranges. Biomarkers with discrete measures, such as genotype locus, will be summarized in frequency tables. Correlative analyses may be performed to investigate associations between biomarkers and clinical endpoints.

3. Table of Contents

MONARCH 2: A Randomized, Double-Blind, Placebo-Controlled, Phase 3 Study of Fulvestrant with or without Abemaciclib, a CDK4/6 Inhibitor, for Women with Hormone Receptor-Positive, HER2-Negative Locally Advanced or Metastatic Breast Cancer

Section	Page
1. Protocol I3Y-MC-JPBL(g) MONARCH 2: A Randomized, Double-Blind, Placebo-Controlled, Phase 3 Study of Fulvestrant with or without Abemaciclib, a CDK4/6 Inhibitor, for Women with Hormone Receptor-Positive, HER2-Negative Locally Advanced or Metastatic Breast Cancer.....	1
2. Synopsis	2
3. Table of Contents.....	7
4. Abbreviations and Definitions.....	14
5. Introduction	19

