10.1.4. Secondary Efficacy Measures

The following secondary efficacy measures (Table JPBL.10.1) will be collected at the times shown in the Study Schedule (Attachment 1).

Table JPBL.10.1. Secondary Efficacy Endpoints

Endpoint	Definition
Overall Survival (OS)	The time from the date of randomization to the date of death from any cause
Objective Response Rate	The proportion of patients with CR or PR according to RECIST v1.1
Disease Control Rate (DCR)	The proportion of patients with CR, PR, or SD according to RECIST v1.1
Duration of Response (DoR)	The time from the date of first evidence of a confirmed CR or PR to the date of objective progression or death from any cause, whichever is earlier
Clinical Benefit Rate (CBR)	The proportion of patients with CR, PR, or SD \geq 6 months according to RECIST v1.1

Abbreviations: CR = complete response; PR = partial response; RECIST = Response Evaluation Criteria in Solid Tumors; SD = stable disease.

Overall Survival (OS): OS duration is measured from the date of randomization of any study drug to the date of death from any cause. For each patient who is not known to have died as of the data-inclusion cutoff date for a particular analysis, OS will be censored for that analysis at the date of last contact prior to the data inclusion cutoff date (contacts considered in the determination of last contact date include AE date, lesion assessment date, visit date, and last known alive date).

Objective Response Rate: The objective response rate is the percentage of patients with a best response of CR or PR.

Duration of Response (DoR): The DoR time is defined only for responders (patients with a confirmed CR or PR). It is measured from the date of first evidence of CR or PR to the date of objective progression or the date of death due to any cause, whichever is earlier. For clarity, the start date should be determined by the initial assessment of CR or PR, not the date of confirmation of CR or PR. If a responder is not known to have died or have objective progression as of the data inclusion cutoff date scores, duration of response will be censored at the last complete objective progression-free disease assessment date.

Disease Control Rate (DCR): The DCR is the percentage of patients with a best response of CR, PR, or SD.

Clinical Benefit Rate (CBR): The CBR is the percentage of patients with a best response of CR or PR, or SD for at least 6 months.

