10.3.3.4. Interstitial Lung Disease/Pneumonitis

Interstitial lung disease/pneumonitis has been identified as an adverse drug reaction for abemaciclib. The majority of events observed in clinical trials were Grade 1 or Grade 2 with serious cases and fatal events reported. Additional information is available in the IB.

Ask your patients to report any new or worsening pulmonary symptoms such as dyspnea, cough, and fever, and investigate and treat as per your local clinical practice (including corticosteroids as appropriate). If ILD/pneumonitis is suspected, investigations may include imaging, such as high-resolution computed tomography, bronchoalveolar lavage, and biopsy as clinically indicated.

Refer to [Table JPBL.9.2](#) for guidance on dose adjustments of abemaciclib for patients with ILD/pneumonitis (see [Attachment 9](#) for ILD/pneumonitis CTCAE grades). Discontinue abemaciclib in cases of severe (Grade 3 or 4) ILD/pneumonitis.

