4.2. Definition

The OS time is measured from the date of randomization to the date of death from any cause. For each patient who is not known to have died as of the data-inclusion cut-off date for a particular analysis, OS will be censored for that analysis at the date of last contact prior to the data inclusion cut-off date.

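### The additional OS analysis in Protocol Section 12.2.9 is really disease-specific mortality with competing deaths censored: rename it and replace its Kaplan-Meier estimate with cumulative incidence

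*Protocol*

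**What the plan says.** Protocol Section 12.2.9 introduces the analysis this way: "An additional OS analysis will also be conducted based on the following definition using similar methods as stated in Section 12.2.8". The definition follows: "time is defined as the time from the date of study enrollment to the date of death due to disease". Deaths from other causes are then handled by this rule: "For patients that have died due to reasons not disease related, survival time will be censored at the date of death".

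Section 12.2.8.1 gives only the hierarchical testing rule for OS and leaves the rest to the SAP. The methods for OS stand in the Protocol synopsis (Statistical Methods, Efficacy). The comparison "will use the log-rank test stratified by stratification variables", and "Additional analyses will be performed using the Kaplan-Meier method to estimate the PFS and OS curves and rates". The same paragraph names a Cox model for the hazard ratio. The SAP addendum, Section 4.3, also names the stratified log-rank test.

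The formal endpoint is defined differently. Protocol Section 10.1.4: "OS duration is measured from the date of randomization of any study drug to the date of death from any cause". SAP addendum Section 4.2: "The OS time is measured from the date of randomization to the date of death from any cause".

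On possible fatal toxicity, Protocol Section 10.3.3.4 calls ILD/pneumonitis an adverse drug reaction of abemaciclib. It says that most events were Grade 1 or 2, with "serious cases and fatal events reported". It gives no fatal rate.

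**The concern.** Two things are wrong. First, the name does not fit the quantity. An analysis that counts only disease deaths is not overall survival as Section 10.1.4 and the SAP addendum define it.

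Second, a patient who dies of another cause can no longer die of the disease. Kaplan-Meier treats her as if she were still at risk and merely unobserved. One minus Kaplan-Meier then estimates a hypothetical risk in a world without other deaths, under independence, and it exceeds the actual probability of disease death.

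The treatment comparison has a related limit. A drug-related death classed as not disease related leaves the event count and enters as a censored time. If such deaths were more frequent on abemaciclib, this analysis would not show it. At stake is how one supplementary result is read and labelled, since OS rates at 1, 2 and 3 years are among the secondary objectives and a curve carrying the OS name invites comparison with them.

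**Working it through.** The plan states no figure for this analysis, so there is none to reproduce.

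**Inputs from the documents**
- Final OS analysis at 441 deaths (Protocol Section 12.1; SAP addendum Section 4.3).
- About 630 patients randomized 2:1 (Protocol Section 8.1), so about 420 and 210.
- All-cause mortality at that point: 441/630 = 0.70.
- Enrollment means assignment to treatment (Protocol Section 4), so the time origin is the same as for OS. Only the event differs.

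**Assumptions**
- Constant hazards for both causes of death.
- Non-disease share of deaths q from 2% to 20%.

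**Step 1: overstatement at 70% mortality.** The cumulative all-cause hazard is −ln(0.30) = 1.204.
- Cumulative incidence of disease death = (1 − q) × 0.70.
- One minus Kaplan-Meier with other deaths censored = 1 − exp(−(1 − q) × 1.204).

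| q | Cumulative incidence | 1 − KM | Excess (points) |
|---|---|---|---|
| 2% | 68.6% | 69.3% | 0.7 |
| 5% | 66.5% | 68.1% | 1.6 |
| 10% | 63.0% | 66.2% | 3.2 |
| 15% | 59.5% | 64.1% | 4.6 |
| 20% | 56.0% | 61.8% | 5.8 |

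**Step 2: overstatement at 36 months.** The assumed medians of 36 and 30 months lie within the 2 to 3 years that the Protocol Introduction gives for metastatic disease.
- Median 36 months, q = 10%: [1 − exp(−0.9 × ln 2)] − 0.9 × 0.5 = 46.4% − 45.0% = 1.4 points.
- Median 30 months, q = 15%: the all-cause cumulative hazard is 1.2 × ln 2 = 0.832. Then [1 − exp(−0.85 × 0.832)] − 0.85 × [1 − exp(−0.832)] = 50.7% − 48.0% = 2.7 points.

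**Step 3: treatment comparison.** Set the control disease-death hazard to 1. Assume a disease-death hazard ratio of 0.80, a background other-cause hazard of 0.05 in both arms, and an excess toxic hazard x on abemaciclib. Then all-cause HR = (0.80 + 0.05 + x) / 1.05. The excess toxic deaths are the abemaciclib deaths times x / (0.85 + x), with total deaths held at 441.

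| x | HR in this analysis | All-cause HR | Excess toxic deaths among 420 |
|---|---|---|---|
| 0 | 0.80 | 0.810 | 0 |
| 0.05 | 0.80 | 0.857 | 286 × 0.05/0.90 = 15.9 |
| 0.10 | 0.80 | 0.905 | 289 × 0.10/0.95 = 30.4 |
| 0.20 | 0.80 | 1.000 | 294 × 0.20/1.05 = 56.0 |

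A second set of assumptions has a disease-death HR of 0.85, with other-cause deaths making up 10% of control deaths and their hazard doubled on abemaciclib. The all-cause HR is 0.9 × 0.85 + 0.1 × 2 = 0.965, against 0.85 in this analysis.

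In this model the all-cause HR is a weighted mean of the two cause-specific HRs. The planned analysis is therefore the more favourable one only when the other-cause HR exceeds the disease HR.

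**Step 4: why one cumulative incidence curve is not enough.** At x = 0.10, the cumulative incidence of disease death is 57.9% on abemaciclib and 69.0% on control, a gap of 11.1 points. One minus Kaplan-Meier gives 62.5% and 70.7%, a gap of 8.2 points. Toxic deaths remove patients who would otherwise die of the disease, so the disease curve alone also flatters the more toxic arm. The curve for other deaths must stand beside it.

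**The case against.** The strongest reply is that nothing important depends on this analysis, and much of that stands.

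- **Fatal toxicity at trial level.** A reader might infer that the plan could hide fatal toxicity in the survival comparison. The documents do not support this. OS in the alpha-controlled hierarchy is death from any cause (Protocol Sections 10.1.4 and 12.2.8.1; SAP addendum Sections 4.2 and 4.3). PFS counts death as an event, subject to the missed-assessment rule in Table JPBL.12.1. Reasons for death on therapy and within 30 days of stopping are summarised (Section 12.2.13). The data monitoring committee sees unblinded safety data (Section 12.2.15.1). The analysis at issue is not part of the OS testing sequence.
- **Validity of the log-rank and Cox results.** A reader might infer that these are biased too. They are not: censoring other deaths is the standard way to address the cause-specific hazard of disease death. Their limit is what they leave out.
- **Methods.** The text says similar methods, not identical ones, and Section 12.2.8.1 names no estimator. Kaplan-Meier is a sound inference from the synopsis. The main SAP (v4, cited in the addendum) is not among the documents here, so further detail there cannot be excluded.
- **Purpose.** Section 12.2.9 ties its sensitivity analyses to the primary endpoint, which is PFS. The OS item sits under that heading but is called only additional. No sentence claims that it tests the robustness of OS.
- **Size.** The non-disease share, the background hazard and the toxic excess are all assumed. Excesses such as 30 or 56 toxic deaths would show in all-cause OS itself.

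The mismatch of name and quantity, the upward bias of one minus Kaplan-Meier, and the lack in these documents of any companion comparison of other-cause death over full follow-up all remain.

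**Conclusion.** The point holds as a minor reporting matter. The analysis is disease-specific mortality under an OS label, and its Kaplan-Meier estimate would overstate the probability of disease death. The overstatement is 0.7 to 5.8 points at 70% all-cause mortality for an assumed non-disease share of 2% to 20%, under constant hazards and on the inference that Kaplan-Meier is used. At the lower end it is negligible.

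The hazard ratio is valid for what it measures. Taken alone as OS it could look better than all-cause OS if other-cause deaths were commoner on abemaciclib. The step 3 figures illustrate that mechanism and do not predict its size. The mention of fatal ILD/pneumonitis shows that such deaths are possible, not how many there would be. The tested OS result, alpha, sample size and primary analysis are untouched.

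**What to change.** In Protocol Section 12.2.9 and the matching SAP text:

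1. Rename the analysis disease-specific (cause-specific) mortality.
2. Replace the Kaplan-Meier estimate with Aalen-Johansen cumulative incidence of disease death and of other death, by arm, in one figure.
3. Keep the stratified log-rank and Cox analysis for disease death, named as cause-specific. Add the cause-specific hazard ratio for other death, and print both beside all-cause OS.
4. State how a death is attributed to the disease and how unknown cause is handled; the documents at hand give no rule.
5. Do not present the analysis as a robustness check on OS.

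The cost is minor wording and one extra figure. The analysis already depends on cause of death, so it calls for no new type of data. Attachment 1 (footnote d) does not list cause of death among the long-term follow-up items, so the sponsor should confirm that it is recorded there.

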12.2.10. Pharmacokinetic and Pharmacodynamic Analyses

Pharmacokinetics analyses will be conducted on all patients who have received at least 1 dose of abemaciclib and have had samples collected (see PK sampling schedule in Attachment 7).

Mean population PK parameters for abemaciclib and its metabolites in plasma (clearance, exposure, volume of distribution, and half-lives) and inter-individual PK variability will be computed using nonlinear mixed effect modeling implemented in NONMEM. The current PK model for abemaciclib, which has been developed using plasma concentration data available from the Phase 1 Study JPBA, will be updated using the plasma data collected in this study. Covariate effects (such as age, weight, sex, creatinine clearance, and plasma protein levels) on the PK parameters of abemaciclib in plasma will also be investigated.

If warranted by the data, mean population PK parameters for fulvestrant in plasma and inter-individual variability estimates will also be computed using nonlinear mixed effect modeling implemented in NONMEM.

Finally, pharmacodynamic data (such as neutrophil, lymphocytes, or platelets counts in blood) collected in this study may be analyzed by means of NONMEM and connected to the population PK model for abemaciclib and/or fulvestrant in a PK/pharmacodynamic model.

The version of software used for the analysis will be documented and will meet the Lilly requirements of software validation.

12.2.11. Tailoring Biomarker Analyses

The distributions of biomarkers with continuous measures, such as gene or protein expression, will be described. Summary statistics will include means, medians, corresponding standard

errors, quartiles, and ranges. Biomarkers with discrete measures, such as genotype locus, will be summarized in frequency tables. Correlative analyses may be performed to investigate associations between biomarkers and clinical endpoints as deemed appropriate.

12.2.12. Health Outcome/Quality of Life Analyses

Patient-reported outcomes are measured through paper versions of the following:

- mBPI-sf (modified Brief Pain Inventory, Short Form)
- EORTC QLQ-C30 (The European Organization for Research and Treatment of Cancer Quality of Life Questionnaire Core 30)
- EORTC QLQ-BR23 (The European Organization for Research and Treatment of Cancer Quality of Life Questionnaire Breast cancer)
- EQ-5D 5L (EuroQol 5-Dimension 5 Level)

For each patient with data from baseline and at least 1 other visit, the maximum change from baseline score will be calculated and summarized for BPI “worst pain”, EORTC composite scores. The reason and number of missing and incomplete questionnaires/assessments by visit will be summarized for each instrument and study arm.

Further analysis details will be described in the SAP.

12.2.12.1. Pain Intensity

Individual pain items on the mBPI-sf (that is, worst, least, average, and current pain) will be described using descriptive statistics by treatment arm. A mixed effects model, repeated measures model may be applied to compare between treatment arms, which will be adjusted for other covariates. Corresponding analyses will also be conducted for the mean of 7 pain interference with function items. If a patient does not complete Questions 5a through 5g on the BPI-sf, the mean score for the 7 pain interference items will be calculated based on those answered questions when at least 4 out of 7 questions were completed (that is, $\geq 50\%$ of the questions were answered).

12.2.12.2. Pain Assessment

Pain analysis will be based on all randomized patients with at least 1 baseline BPI “worst pain” and one BPI “worst pain” score on Cycle 2 Day 1 or later.

The mBPI-sf will be administered at baseline prior to study drug dosing and the Cycle 1, Day 1 score will be treated as a baseline observation and the Day 1 score of each subsequent cycle will be attributed to the previous cycle. The mBPI-sf will be administered at treatment discontinuation and grouped with observations from the previous cycle.

Time to worsening in pain will be described using the method of Kaplan and Meier and will be made between 2 arms by a log-rank test. “Worsening” will be defined as either a “worst pain” increase of ≥ 2 points postbaseline or an analgesic drug class increase of ≥ 1 level. Worsening rate at Years 1, 2, and 3 will be estimated and compared between the 2 arms. Number of events due to each criterion will be described.

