Preliminary safety data from Study JPBH demonstrate that the AE profile of abemaciclib administered in combination with nonsteroidal aromatase inhibitors (NSAIs) is consistent with abemaciclib monotherapy, as the most common TEAEs possibly related to study drug were diarrhea, nausea, fatigue, and neutrophil count decreased. However, at the 200-mg dose, the incidence of treatment-emergent Grade 3 diarrhea was found to be greater when abemaciclib was administered in combination with an NSAID from a review of the preliminary safety data in Study JPBH, compared to abemaciclib administered alone in Part D of Study JPBA. Nevertheless, when the abemaciclib dose was reduced from 200 mg to 150 mg or lower for some patients in Study JPBH, either the severity of diarrhea decreased or the event resolved.

The rationale for the underlying change in the abemaciclib starting dose is, that although the Phase 1 Study JPBA demonstrated that the 200 mg Q12H abemaciclib dose was tolerable when administered in combination with fulvestrant, a substantial number of patients required abemaciclib dose suspension and/or reduction during the first 2 treatment cycles. As a consequence of this observation, a review of dosing and tolerability data from patients enrolled during the first 5 months of this study was carried out as part of a regular blinded safety review to assess if a similar number of patients required dose alterations in the present study. During the review of blinded safety data from Study JPBL, any alteration in dosing of abemaciclib or placebo was presumed to have occurred on the abemaciclib arm. The data review did reveal a high number of dose alterations for abemaciclib or placebo. The cause of this was principally diarrhea occurring in the first treatment cycle. Therefore, the initial dose of blinded study drug administered in combination with fulvestrant will be reduced to 150 mg Q12H.

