10.2.1.1. Pain Intensity

The mBPI-sf (Cleeland 1991) is an 11-item instrument used as a multiple-item measure of cancer pain intensity. In addition to pain intensity (4 items), the mBPI-sf is designed for patients to record the presence of pain in general, pain relief, and pain interference with function (general activity, mood, ability to walk, ability to perform normal work, relations with others, sleep, and enjoyment of life).

Responses for the mBPI-sf items are captured through the use of 11-point numeric rating scales anchored at 0 (*no pain or does not interfere*) and ranged through 10 (*pain as bad as you can imagine or completely interferes*). The mBPI-sf recall period is 24 hours, and typical completion time for this instrument is less than 5 minutes. Focused analysis will be on “worst pain”.

Use of pain medication will be assessed in conjunction with the mBPI-sf assessment. Data on each individual prescription and over-the-counter analgesic medication will be recorded on the Concomitant Medications eCRF. The use of pain medications should be reviewed with the patient at each subsequent visit. Any changes to analgesic use (new or stopped analgesics) will be recorded on the eCRF. Pain medication will be classified into medication categories, using the World Health Organization analgesic ladder. A medication category will be assigned based on the maximum analgesic therapy administered for that cycle on a routine basis.

The BPI population will include all patients who completed at least 1 baseline followed by at least 1 BPI “worst pain” postbaseline assessment.

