OS is an important secondary endpoint for this study. OS will be tested only if the test of PFS is significant. The final OS analysis will be conducted at 441 OS events in the EP stratum (see Section 12.2.8 for details).

Prior to Amendment (b), no more than 100 patients were to be enrolled into the EN stratum. Amendment (b) removes the inclusion of EN patients and specifies that the previously enrolled EN patients will not be included in the primary analysis. It is anticipated that approximately 50 patients will be enrolled into this stratum.

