12.2. Statistical and Analytical Plans

12.2.1. Analysis Populations

The ITT population will be comprised of all randomized patients randomized within the EP strata (either primary endocrine resistance or secondary endocrine resistance), per IWRS.

The safety population will include all randomized EP patients who receive at least one dose of any study drug.

Patients randomized within the ‘no prior endocrine therapy’ stratum comprise the EN population. Exploratory efficacy analyses will be performed on this population. The EN safety population will include all randomized EN patients who receive at least one dose of any study drug.

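### The pain analysis set is not limited to the ITT (EP) population, and it excludes any patient with a Cycle 1 analgesic increase who gives no later qualifying pain score

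*Protocol*

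**What the plan says.** Protocol section 12.2.12.2 defines the set for the pain analyses: "Pain analysis will be based on all randomized patients with at least 1 baseline BPI" worst-pain value and another such "score on Cycle 2 Day 1 or later". The same section defines worsening as either a rise of at least 2 points in worst pain or "an analgesic drug class increase of" at least one level. It plans Kaplan-Meier curves, a log-rank comparison of the arms, and worsening rates at Years 1, 2 and 3.

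Other sections bear on who belongs in that set:

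- Section 12.2.1: "The ITT population will be comprised of all randomized patients randomized within the EP strata". EN patients form a separate population, of which it says: "Exploratory efficacy analyses will be performed on this population".
- Section 12.2.2 ties the ITT population to the primary analyses only, so it does not settle the pain set.
- Section 5.2 says that Amendment (b) refocused the study objectives on EP patients. Section 12.1 says of the EN stratum: "It is anticipated that approximately 50 patients will be enrolled into this stratum".
- Section 10.2.1.1 describes a pain population in other terms: "The BPI population will include all patients who completed at least 1 baseline followed by at least 1 BPI" worst-pain assessment after baseline, with no mention of Cycle 2. It also assigns an analgesic category for each cycle, so Cycle 1 has its own.

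**The concern.** Two things in the definition do not fit the rest of the plan.

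First, elsewhere the protocol names its population. Response rates use ITT (12.2.8.2), the safety population is restricted to EP patients (12.2.1), and the safety interim analyses state that EN patients are included (12.2.15.1). The pain section says only that randomized patients are used, and EN patients were randomized.

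Second, entry to a time-to-event analysis is conditioned on something that happens after randomization. One of the two event criteria needs no questionnaire, so the entry rule can remove a patient who has already had the event. A log-rank comparison does not need such a rule, because patients without later data can be censored.

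At stake is the main between-arm comparison for pain. Section 10.2.1 names palliation of pain as the primary health-outcomes goal, and section 6.2 lists pain among the secondary objectives.

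**Working it through.** **The plan's own figure.** Section 12.1 gives the EP stratum as 450 + 180 = 630, which reproduces. The documents state no sample size or power for the pain analysis.

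**EN share of the literal set** (before the score requirement is applied) = EN / (EP + EN).

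- With the expected 50 EN patients: 50 / (630 + 50) = 50/680 = 7.4%.
- With the cap of 100 that applied before Amendment (b): 100 / (630 + 100) = 100/730 = 13.7%.

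**Effect of EN patients on a worsening rate.** If the EN rate differs from the EP rate by d, the pooled rate differs from the EP rate by d × (EN share). The documents give no EN worsening rate, so d is an assumption.

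- 50 EN patients: d = 5, 10 or 20 points moves the pooled rate by 0.4, 0.7 or 1.5 points.
- 100 EN patients: the same values move it by 0.7, 1.4 or 2.7 points.

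Section 5.2 confirms that patients with no prior endocrine therapy were a separate level of the stratification factor. Including them therefore changes who is described but not the balance between arms.

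**Patients removed by the score requirement.** At 2:1, 630 EP patients split into about 420 on abemaciclib and 210 on placebo. The documents give no rate of missing later scores, so these rates are assumed:

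- abemaciclib: 2%, 5% or 10% of 420 = 8, 21 or 42 patients;
- placebo: 1%, 3% or 5% of 210 = 2, 6 or 11 patients.

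**Effect on one arm's worsening proportion.** Let a share q be removed, with worsening proportion w among those removed and r among those kept. The full-arm proportion minus the kept-set proportion is q × (w − r). With r = 0.40 assumed:

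- q = 2%: 0, 0.4 or 0.8 points for w = 0.4, 0.6 or 0.8;
- q = 5%: 0, 1.0 or 2.0 points;
- q = 10%: 0, 2.0 or 4.0 points.

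If w is below r, the sign reverses. The effect on the comparison depends on q and w in each arm, and the documents give neither.

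**Who is excluded for certain.** Footnote k of Attachment 1 schedules the questionnaire at baseline, at Cycle 2 Day 1, at set later cycles and at short-term follow-up. Section 12.2.12.2 adds one at treatment discontinuation, grouped with the previous cycle.

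Short-term follow-up ends 30 ± 5 days after the decision to stop. A patient stopping on Day 1 of Cycle 1 would nominally be seen near Day 31, which is after Day 29, the planned Cycle 2 Day 1. At the early edge of the window the visit falls on the stopping day + 25, which is before Day 29 only for stopping on Days 1 to 3.

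By calendar time, then, nearly all Cycle 1 leavers who complete the follow-up questionnaire could qualify. The text does not say whether a calendar reading is meant for someone who never starts Cycle 2. On any reading, a patient with no later score is excluded.

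**The case against.** The strongest case against the point is that little is lost and that the full SAP may settle it.

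- **The two pain populations.** Section 12.2.12.6 explains a post-baseline visit as one on or after Day 1 of Cycle 2, and no routine questionnaire falls between baseline and that visit. The wordings in 10.2.1.1 and 12.2.12.2 are therefore close to equivalent. This stands. What remains is how a score taken at discontinuation during Cycle 1 is treated.
- **Convention.** All the patient-reported sets require a baseline and a later score, and section 12.2.12 has missing questionnaires and their reasons summarized by arm. That makes uneven loss visible, but it does not restore events already removed.
- **EN patients.** Section 5.2 states the EP focus, so the sponsor may never have intended to include EN patients. The analysis text nevertheless includes them.
- **Missing SAP.** Section 12.2.12 defers details to the SAP. Only the overall-survival addendum was available, and it cites a SAP v4 that was not. That document may define the set, in which case the protocol wording still needs to match it.

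A reader might infer more than the documents support.

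- One inference is that Cycle 1 analgesic increases are discarded in general. They are not: they count for every patient who has a qualifying later score.
- Another is that treatment-related early leavers are dropped and that abemaciclib is thereby flattered. Section 5.1.1 says of the early dose alterations: "The cause of this was principally diarrhea occurring in the first treatment cycle". Those were alterations seen in a blinded review at the 200 mg start and presumed to be on abemaciclib. They were not withdrawals or missing questionnaires. Nothing links them to analgesic use, and many early leavers may qualify through later questionnaires.

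**Conclusion.** The point holds in two parts.

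1. As written, the pain set is not restricted to ITT (EP). It includes about 50 EN patients, 7.4% of 680 randomized. On assumed EN-EP differences of 5 to 20 points, pooled worsening rates would move by about 0.4 to 1.5 points. This is a question of which population is described, not of imbalance between arms.
2. Membership depends on a post-randomization score, so a patient with a Cycle 1 analgesic increase and no later qualifying score is excluded although the event definition is met. The number of such patients and the direction of any bias cannot be determined from the documents. The figures above for removed patients are illustrations on assumed rates.

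The likely effect is modest. The correction is still worth making, because the text as it stands yields a different population from the one the trial now addresses and can lose real events. The conclusion rests on a literal reading of 12.2.12.2 and would change if SAP v4 defines the set otherwise.

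**What to change.** Amend section 12.2.12.2 as follows.

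- Base the pain analysis on the ITT population (EP strata, per IWRS) with a baseline worst-pain score. Report EN patients separately as exploratory.
- In time to worsening, keep patients who have no later score. Count an analgesic class increase as an event on its date. Otherwise censor at the last date on which pain or analgesic use was assessed, and at randomization only if there is no post-baseline information. Censoring every non-scorer without an event at randomization would keep their events while discarding known event-free time, since section 9.6 has concomitant medication recorded through discontinuation and the 30-day visit.
- State whether scores at treatment discontinuation and at short-term follow-up qualify, including for patients who never start Cycle 2.
- Align the BPI population in section 10.2.1.1, and the SAP, with this wording.

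The cost is a changed analysis-set flag and slightly more derivation work, for example dating an analgesic increase when the category is assigned by cycle. The comparison has about 50 fewer (EN) patients. All the data needed are already collected.
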